As of May 2019 in Study 5F9005, clinical activity was assessed for magrolimab monotherapy in R/R AML/MDS and for magrolimab in combination with azacitidine in TN/U AML/MDS (Sallman 2019). Magrolimab monotherapy induced an objective response in 1 of 10 (10%) R/R AML/MDS patients (with 1 AML patient achieving morphologic leukemia-free state [MLFS]). With magrolimab in combination with azacitidine, 11 of 11 (100%) MDS patients achieved an objective response, with a CR+partial remission (PR) rate of 55%. In untreated AML patients, magrolimab in combination with azacitidine induced an objective response in 9 of 14 (64%) of patients, with 36% achieving a CR and 14% achieving a CR with incomplete blood count recovery (CRi). Median time to response at 1.9 months for the combination treatment was more rapid than that expected for azacitidine alone (4 to 6 months). In MDS patients, 3 of 7 (43%) responding patients with abnormal cytogenetics at baseline

achieved a complete cytogenetic response, with 2 of 10 responders with minimal residual disease (MRD) assessment achieving MRD negativity by flow cytometry. In summary, in a limited sample size, magrolimab in combination with azacitidine has meaningful clinical activity that appears to be enhanced compared to azacitidine monotherapy. Further results are found in the IB.

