#### 10. MEASUREMENT OF EFFECT

Assessment of response will be conducted by the Investigator using the criteria in Appendix B, which are based primarily on the 2017 ELN recommendations for AML (Döhner 2017) and the 2003 IWG criteria (Cheson 2003) for AML patients. Response classifications include: complete remission (CR) rate, morphologic CR, complete remission without minimal residual disease (CRMRD-), cytogenetic complete remission (cCR), molecular complete remission (mCR), complete remission with incomplete hematologic recovery (CRi), complete remission with partial hematologic recovery (CRh), marrow complete remission (CR), morphologic leukemia-free state (MLFS), PR, and stable disease (SD).

In addition, hematologic improvement (HI) will be assessed by 2006 IWG criteria (Cheson 2006) to compare with disease response assessed by 2017 ELN criteria (Döhner 2017) and 2003 IWG criteria (Cheson 2003).

Response will be assessed in MDS patients using the criteria in Appendix B Table 14-4, which are based on the 2006 IWG criteria (Cheson 2006) with the added caveat that the impact of anemia must be deemed disease-related and not due to study treatment.

Response assessments will be performed at the time points specified in the Schedule of Assessments in Section 7.1 and as described in Section 7.9.

The following summary measures for endpoints will be evaluated:

**Objective Response Rate for Patients with AML**: The ORR is the proportion of patients who reach CR (including morphologic CR, CRMRD-, cCR, and mCR), CRi, CRh, PR, or MLFS while on study.

**CR Rate for Patients with AML**: The CR rate is the proportion of patients who achieved CR, as defined by the Investigator based on ELN AML recommendations (Döhner 2017; Appendix B).

**CR Rate for Patients with MDS**: The CR rate is the proportion of MDS patients who reach morphologic CR while on study per IWG 2006 criteria (Cheson 2006).

**Duration of Complete Remission (DCR) for AML**: The DCR is measured from the time measurement criteria are first met for CR (including morphologic CR,  $CR_{MRD}$ -, cCR, and mCR) until the first date that recurrent disease or death with evidence of no disease recurrence is objectively documented. Those who are not observed to have recurrent disease or die with evidence of no recurrence during the trial active period will be censored at their last response assessment date with evidence of no progression/recurrence.

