## 11.4. Sample Size Determination

The number of patients planned for inclusion in this trial is up to a total of approximately 287 patients evaluable for efficacy, as follows:

- R/R Safety Cohort: 10 patients
- R/R Expansion Cohort: Up to 36 patients
- R/R MDS Magrolimab Monotherapy Cohort: 23 patients
- TN/U Dose Evaluation Cohort: Up to 18 patients
- TN/U Expansion Cohort: Up to 172 patients, including
  - Original 30 TN/U Expansion (enrolled 18 AML and 16 MDS patients, including 4 replacement patients)
  - At least 92 MDS patients (including the original 16 MDS patients enrolled in the original TN/U Expansion), of whom at least 56 patients will be on Q2W dosing. The overall MDS expansion to 92 patients will be considered the MDS Registrational Cohort.
  - Up to 62 TP53 mutant AML patients (i.e., 12 original TP53 mutation AML patients, plus 20 additional TP53 mutant AML patients added per CTSC decision in September 2019, plus 30 additional TP53 mutant AML patients per CTSC decision July 2020)
- RBC Transfusion-dependent Low-risk MDS Cohort: Up to 20 patients
- Rollover Cohort: Up to 8 patients

For the R/R Safety Cohort, 10 patients have been enrolled as of the approval of Amendment 5 for evaluation of safety of magrolimab monotherapy.

For the R/R Safety Cohort and Expansion Cohort, approximately 46 patients may be enrolled, including 10 patients treated in the safety run-in cohort and 36 patients treated in the expansion cohort. For the R/R Safety Cohort, 10 patients were enrolled and this cohort was closed to further enrollment as of Amendment 3. Based on safety and efficacy data, the CTSC may decide to expand the R/R Expansion Cohort to include additional patients. An ORR of 17% has been reported in patients with R/R AML who have been treated with azacitidine (Itzykson 2015). For an estimated response rate of 33% or higher, 36 patients would provide a 95% confidence interval, with the lower bound to exclude 18.6%, the azacitidine monotherapy efficacy rate.

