assessment (Cycle 3 Day 1); however, enrollment will continue and not be paused in the interim. A sample size of 36 patients provides 80% power to reject the null hypothesis that the CR rate is 16.5% or lower at 2-sided 0.05 significant level, assuming the true magrolimab + azacitidine CR rate is at least 35.5% (19% improvement). The null CR rate of 16.5% is based on the pivotal randomized trial leading to azacitidine approval in MDS reanalyzed by IWG 2000 criteria (Silverman 2006), where the upper bound of the 1-sided 95% confidence interval for azacitidine CR rate is 16.5%, with a point estimate of 10%. Based on Amendment 6 and FDA feedback for a single-arm trial to support a potential BLA, the sample size of the TN/U MDS-only Expansion Cohort for untreated, higher-risk MDS patients was further increased to include a cohort of 56 patients with MDS at a magrolimab Q2W dosing regimen. A sample size of 56 patients provides 80% power to reject the null hypothesis that the CR rate is 16.5% at a 2-sided 0.05 significant level, assuming the true magrolimab+azacitidine CR rate is at least 31.5%. The null CR rate of 16.5% is based on the same assumption for azacitidine monotherapy as above. A combined planned sample size of 92 patients for the MDS Registrational Cohort will provide an 80% power to reject the updated null CR rate of 23.5% at a 2-sided 0.05 significant level, assuming the true magrolimab+azacitidine CR rate is 36.5%.

Per the CTSC decision in September 2019 and Amendment 6, a subcohort of TP53 mutant TN/U AML patients was added. Initially, 12 patients and then an additional 20 patients will be enrolled. Analysis of these patients will include all TP53 mutant patients meeting subcohort eligibility enrolled prior to the Amendment/CTSC decision. A sample size of 32 patients was selected to evaluate the initial efficacy of magrolimab+azacitidine as compared to available therapies (most notably venetoclax+hypomethylating agents) in TP53 mutant AML. While venetoclax in combination with hypomethylating agents (azacitidine or decitabine) is approved in newly diagnosed AML patients who are ineligible for intensive chemotherapy, their efficacy in TP53 mutant AML patients is limited. Per a recent report, the CR+CRi rate of venetoclax+hypomethylating agent in TP53 mutant AML was 47%, with a median duration of CR of 5.6 months and a median overall survival of 7.2 months (DiNardo 2019). In contrast, in all-comer AML patients, the CR+CRi rate was 67% with

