a median duration of CR of 11.3 months and a median overall survival of 17.5 months. Assuming an observed magrolimab+azacitidine ORR of 59% for a sample size of 32 patients, the 1-sided 90% confidence interval will have a lower bound of 46.5%, which excludes a control ORR of 46%. Based on emerging data, the CTSC may decide to enroll additional patients for further safety, efficacy, or dosing information. Per CTSC decision in July 2020 and captured in Amendment 7, an additional 30 TP53 mutant AML patients were enrolled for the TN/U Expansion Cohort (n = 62).

For the RBC Transfusion-dependent Low-risk MDS Cohort, approximately 20 patients will be enrolled. Initially, 6 patients will be enrolled with a safety evaluation after all 6 patients complete at least Cycle 2 Day 15 treatment. This safety evaluation is being conducted given that a 60 mg/kg dose of magrolimab will be administered starting in Cycle 2, of which this highest dose has not yet been tested in MDS patients. However, an equivalent dose of 60 mg/kg given in 1 week (30 mg/kg twice weekly) has already been administered to MDS and AML patients in this trial and has been well tolerated. The CTSC will then evaluate based on the aggregate safety profile in these 6 patients and determine whether enrollment should proceed to the remaining 14 patients. If so, these 14 patients can be simultaneously enrolled. Based on emerging data, the CTSC may decide to enroll additional patients for further safety, efficacy, or dosing information. These may be enrolled as either magrolimab monotherapy or in combination with azacitidine.

For the Rollover Cohort, 1 eligible patient from the Phase 1 study (SCI-CD47-002) is now enrolled in this study, and this cohort was closed to further enrollment as of Amendment 3.

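### The TP53 sample-size justification measures its 46.5% lower bound against an unsourced 46% instead of the cited 47% comparator, and the R/R Expansion text labels its own lower limit, 18.6%, as the azacitidine rate

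*Protocol*

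**What the plan says.** **TP53 mutant AML.** Protocol section 11.4 explains the size of the subcohort: "A sample size of 32 patients was selected to evaluate the initial efficacy of magrolimab+azacitidine as compared to available therapies". For the comparator it reports that "the CR+CRi rate of venetoclax+hypomethylating agent in TP53 mutant AML was 47"%. The precision statement starts from a supposed result: "Assuming an observed magrolimab+azacitidine ORR of 59% for a sample size of 32 patients". From this it concludes that "the 1-sided 90% confidence interval will have a lower bound of 46.5%, which excludes a control ORR of 46"%. The Synopsis (Sample Size Justification) has the same text. Section 11.4 then records that 30 more patients were added by steering committee decision, for a total of 62.

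**Endpoint definition.** Section 10 defines ORR in AML as CR in its several forms together with "CRi, CRh, PR, or MLFS while on study".

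**The trial's own AML data.** Section 1.2.2.3 reports, for untreated AML on the combination, "an objective response in 9 of 14 (64%) of patients, with 36% achieving a CR and 14% achieving a CR"; the last figure there, 14%, is CRi.

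**R/R Expansion.** Section 11.4 and the Synopsis first state: "An ORR of 17% has been reported in patients with R/R AML who have been treated with azacitidine". The precision statement for a 33% response rate in 36 patients then runs "with the lower bound to exclude 18.6%, the azacitidine monotherapy efficacy rate".

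**The concern.** In each justification the figure to be excluded is not the benchmark the protocol cites.

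For TP53, the cited comparator is 47% and the figure said to be excluded is 46%. The stated bound of 46.5% falls between the two, so the conclusion depends on which is used. The two sides also measure different things: the comparator is CR+CRi, while the trial's ORR adds further response categories, mainly PR and MLFS.

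For R/R Expansion, 17% is cited and 18.6% is then given the name of the azacitidine rate.

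The stake is the stated reason for the TP53 sample size. A reader would take 19 responders in 32 as enough to rule out the venetoclax-based comparator, and on the protocol's own figures it is not.

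**Working it through.** **Inputs**
- TP53: n = 32; observed ORR 59%, nearest count 19/32 = 59.4%; 1-sided 90% interval; stated bound 46.5%; control used 46%; comparator cited 47% CR+CRi (section 11.4, Synopsis). Enlarged cohort n = 62.
- R/R Expansion: n = 36; assumed rate 33%, i.e. 12/36; 95% interval; cited azacitidine ORR 17%; figure called the azacitidine rate 18.6% (section 11.4, Synopsis).
- Untreated AML data: ORR 9/14, CR 36% (5/14), CRi 14% (2/14) (section 1.2.2.3).

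**Step 1. Reproduce the TP53 bound.** The exact (Clopper-Pearson) lower limit for x responders in n is the α quantile of a Beta(x, n − x + 1) distribution. With x = 19, n = 32 and α = 0.10, the 0.10 quantile of Beta(19, 14) is 46.51%. This matches the stated 46.5%. Other 1-sided 90% bounds for 19/32 do not: Wald 48.2%, Wald with continuity correction 46.7%, Wilson 48.1%. The protocol's figure is therefore the exact one, and it is correct.

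**Step 2. Compare it with the cited control.** 46.5% is above 46% and below 47%. By the same method:

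| Responders | Rate | Exact 1-sided 90% lower bound | Excludes 47%? |
|---|---|---|---|
| 19/32 | 59.4% | 46.5% | no |
| 20/32 | 62.5% | 49.6% | yes |
| 34/62 | 54.8% | 45.9% | no |
| 35/62 | 56.5% | 47.5% | yes |
| 37/62 | 59.7% | 50.7% | yes |

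**Step 3. Can 46% be the comparator's ORR?** By section 10, ORR counts every CR and CRi and adds other categories. On that definition a regimen with 47% CR+CRi has an ORR of at least 47%, so 46% is not possible.

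**Step 4. Effect of the endpoint mismatch.** Suppose the regimen only equals the comparator, with a true CR+CRi of 47%. The chance of meeting the illustrated result is P(X ≥ 19), with X binomial(32, p) and p equal to 47% plus the amount by which ORR exceeds CR+CRi.

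| Assumed gap (points) | p | P(X ≥ 19) |
|---|---|---|
| 0 (matched endpoints) | 47% | 11% |
| 2 | 49% | 16% |
| 5 | 52% | 26% |
| 10 | 57% | 47% |
| 14 | 61% | 65% |

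The gaps are assumptions. The protocol's only data on the gap are 9/14 − (5 + 2)/14 = 2/14, or 14 points, with an exact 95% interval of about 2% to 43%. Those patients had untreated AML in general and were not a TP53 group.

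**Step 5. R/R Expansion.** The exact 2-sided 95% lower limit for 12/36 is the 0.025 quantile of Beta(12, 25), which is 18.56% and rounds to 18.6%. The figure called the azacitidine rate is thus the lower limit of the trial's own assumed result. That limit lies above the cited 17%.

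**The case against.** The strongest reply is that these are precision illustrations and not decision rules. A reader might infer that a regimen no better than the comparator would be declared superior to it. The protocol does not support that inference. The primary AML endpoint is the CR rate, reported with a 95% confidence interval; the only test written out in section 11.8.1.1 is for higher-risk MDS; and no TP53 success rule is given. This part of the reply stands in full.

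Further points that stand:
- It would be wrong to say the bound excludes nothing. It excludes 46% and everything below it.
- The slip from 47% to 46% is small in itself: P(X ≥ 19) is 9.0% at a true 46% and 11.0% at 47%, and the cost is one responder.
- The 65% should not be quoted alone. It rests on 2 of 14 patients outside the TP53 group, which is why a range is shown.
- CRh overlaps largely or wholly with CRi as Appendix B defines them, so the real additions in ORR are mainly PR and MLFS.
- The text on 32 patients is an accurate account of the initial plan and is not an error because 62 were planned later. At n = 62, about 59% observed (37/62) would clear 47% on the exact bound.
- A reader might argue that 12/36 fails an 18.6% benchmark and that 13/36 is needed. That compares 18.56% with its own rounded value and has no substance.
- The schedules of assessments mark both expansion cohorts as closed to enrollment, so the rationale no longer drives accrual.

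A Wald or Wilson bound for 19/32 (about 48%) would exclude 47%. That does not rescue the sentence, because neither method gives the 46.5% that the protocol states. What the reply leaves untouched is that the figures are wrong as written, and that the endpoint mismatch favours the trial.

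**Conclusion.** The point holds as a correction to two stated benchmarks, of minor to moderate severity.

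On the exact method that reproduces the protocol's own bound, 59% of 32 does not exclude the comparator the protocol cites. It falls short by half a percentage point (46.5% against 47%), or one responder. The 46% has no source and is incompatible with the protocol's ORR definition.

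The endpoint mismatch is potentially the larger matter. Its direction follows from the definition of ORR, but its size is not known: the chance of reaching 19/32 at a true CR+CRi of 47% is 11% when endpoints match and 16% to 65% for assumed gaps of 2 to 14 points.

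The R/R figure is a labelling error with no design consequence, since 12/36 does exclude the cited 17%.

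**What to change.** In section 11.4 and the Synopsis:

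1. **TP53 control.** Replace the 46% with the cited 47%, and compare CR+CRi of the combination with CR+CRi of the comparator.
2. **TP53 precision statement.** Restate it as 20/32 (62.5%, exact 1-sided 90% lower bound 49.6%) or, for the enlarged cohort, 35/62 (56.5%, lower bound 47.5%).
3. **R/R Expansion.** Say that 12/36 (33.3%) has an exact 95% lower limit of 18.6%, which excludes the reported azacitidine ORR of 17%.

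The cost is a wording change in two places. The illustrated TP53 hurdle at n = 32 rises by one responder and is read on a narrower endpoint. No sample size, formal test, primary analysis or patient procedure changes.

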### 11.5. Clinical Trial Steering Committee

The CTSC will oversee the conduct of the clinical trial. A representative from the Sponsor, usually the Study Medical Monitor or designee, will chair the CTSC. The CTSC will have representation from each participating site in the study. The CTSC will review safety and efficacy data generated during the trial and make decisions about patient recruitment, trial management, initiation of protocol specific amendments,

expansion of cohorts, using higher or lower dose levels or different dosing schedules, defining any new dose cohorts, and identification of the recommended dose and schedule for Phase 2 trials. The CTSC will meet at a minimum at the completion of each dosing cohort during safety run-in and dose evaluation phase of the trial and when emergent critical safety data are reported. The composition, structure, and function of the CTSC are defined in the CTSC Charter.

CTSC decisions in this study are included in the following sections of this document: Section 3.1 Overall Study Design; Section 3.2 Study Design - R/R Cohort; Section 3.3 Study Design - TN/U Cohort; Section 3.4 Study Design - RBC Transfusion-dependent Low-risk MDS Cohort; Section 3.5 Study Design - Rollover Cohort; Section 3.7 Estimated Study Duration and End of Study; Section 6.1 Study Drug Administration; Section 6.2.1.1 Dose Modification and Delay Guidelines, magrolimab; Section 7.3.8 Bone Marrow Assessments; Section 7.10 Pharmacokinetics; Section 7.12 Pharmacodynamic and Biomarker Assessments; and Section 11.8.2 Additional Secondary Endpoints.

# 11.6. Data Monitoring Committee

Data Monitoring Committee functions for this trial will be performed by the CTSC, as defined and described in Section 11.5.

## 11.7. Analysis of the Conduct of the Study

The CTSC, in conjunction with the Sponsor, will be the main body responsible for the analysis of the conduct of the study, as outlined in the CTSC Charter.

### 11.8. Statistical Methods

All analyses will be conducted separately for patients by indication in the R/R Cohorts, the TN/U Cohorts, and the Rollover Cohort, unless otherwise mentioned. Additional analyses may be conducted separately for the R/R Safety Cohort alone and TN/U Dose Evaluation Cohorts. Combined safety analyses may be conducted for patients in both monotherapy cohorts (the R/R Safety Cohort, R/R MDS Cohort, and Rollover Cohort, where applicable), as well across the study on all treated patients. Statistical analyses

will be performed separately for the patients treated with magrolimab in combination with azacitidine in the TP53 TN/U AML Cohort and RBC Transfusion-dependent Low-risk MDS Cohort, as well as in the untreated higher-risk MDS cohort as a potential pivotal single-arm study to support a potential BLA in higher-risk untreated MDS.

For continuous variables, the mean, standard deviation, median, and ranges will be provided. For categorical variables, the frequency and percentage in each category will be provided, along with 95% confidence intervals for primary and secondary efficacy endpoints. For time-to-event variables, the Kaplan-Meier (KM) estimates and corresponding 2-sided 95% confidence intervals for the median will be provided, when appropriate. The KM plots may also be provided. Details regarding the statistical analysis to be conducted, including the handling of missing data and patient withdrawal, will be provided in the SAP.

### 11.8.1. Efficacy Analyses

## 11.8.1.1. Primary Efficacy Endpoint: CR Rate

The primary efficacy endpoint for both AML and MDS is CR rate as assessed by Investigators. The analysis of CR rate will be conducted on all enrolled patients who receive at least 1 dose of the investigational drug magrolimab. In addition, an evaluable patient efficacy analysis will be performed on all enrolled patients who receive at least 1 dose of magrolimab and have at least 1 disease response assessment or who died before the first post-treatment disease response assessment. The point estimate of the CR rate and the corresponding 2-sided 95% confidence interval will be generated.

For the primary analysis of TN/U higher-risk MDS patients, the percentage of patients achieving a CR will be estimated based on all TN/U higher-risk MDS patients who received at least 1 dose of magrolimab, with exact 95% CI using the Clopper and Pearson method. Formal hypothesis testing will be performed to test the statistical hypothesis of:

 $H_0$ : CR rate = 23.5%; vs.

 $H_1$ : CR rate ≠ 23.5%.

The Chi-square test will be performed at 2-sided 0.05 significance level.

### 11.8.1.2. Secondary Efficacy Endpoints

Additional parameters of objective response, including CRh, will be evaluated in a similar manner as the primary efficacy endpoints. For the time-to-event endpoints listed here, the Kaplan-Meier (KM) estimates and corresponding 95% intervals for the median will be provided when appropriate. The KM plots may also be provided when appropriate. RBC transfusion independence is defined as no transfusions for at least an 8-week consecutive period. The percent of patients who become RBC transfusion-independent will be estimated based on the number of patients who received at least 1 dose of HuF59-G4 and are RBC transfusion-dependent at baseline.

### **Duration of Complete Remission (DCR)**

The analysis of DCR will be conducted using the Kaplan-Meier method.

### **Progression-free Survival (PFS)**

The analysis of PFS will be conducted on all treated patients.

## Overall Survival (OS)

The analysis of OS will be conducted on all treated patients.

### Objective Response Rate (ORR) and Duration of Response (DOR)

Analysis of ORR and DOR will be conducted in the R/R MDS Magrolimab Monotherapy Cohort.

